Document Date: 10.01.2020

NCT: NCT03436147

Vaginal-assisted laparoscopic sacrohysteropexy (VALH) and vaginal hysterectomy+vaginal vault suspension (VH+VVS) for advanced uterine prolapse: 12month preliminary results of a randomized controlled study Materials and Methods

In this study, the first-year results of a single-center, randomized controlled study of two parallel groups, conducted in the tertiary referral training and research hospital, were evaluated. The study included women who were admitted to our urogynecology unit for stage 2–4 symptomatic uterine prolapse between June 2017 and January 2019. The study was approved by our hospital's local ethics committee (approval number: 2018/23).

Requirements for participation were that the women be over 18 years of age with no desire to preserve fertility (subjects had completed childbearing or were practicing reliable contraception), have a normal size uterus (< 10 cm) on examination or ultrasound, and agree to participate in principle. They were then given further information about the trial, and consent was sought either in an outpatient clinic or at the next visit for preoperative assessment. Exclusion criteria were: cervical elongation (surgeon's discretion), prior prolapse surgery, current foreign-body complications, increased risk or recent history of cervical dysplasia, chronic pelvic pain, significant uterine abnormalities, abnormal menstruation or postmenopausal bleeding within the previous 12 months, and a significantly enlarged fibroid uterus or concomitant medical problems precluding general anesthesia or the assumption of a steep Trendelenburg position. Written informed consent was obtained from all of the participants.

Participants were randomly assigned to either of two groups: Group A (VALH) or Group B (VH+VVS). The consolidated standard of reporting trials (CONSORT) flow study diagram is presented in Figure 1. Simple randomization was performed by the distribution of blind envelopes in order to separate the patients into the groups; this randomization was performed before admission to surgery. Those who subsequently had a strong preference for either operation and consequently declined to continue in the study were excluded and not put through the randomization process.

Age, parity, body mass index (BMI), intraoperative blood loss, operation time, and postoperative hospital stay were recorded. Blood loss was assessed by volume of blood and the weight of soaked pads. BMI was calculated as the weight (kg) divided by the square of the height (m²).

Surgeries were performed under general anesthesia with the help of residents and one specialized urogynecologist. The VALH operation was initiated with conventional laparoscopy. Then, one 10 mm umbilical and two 5 mm lower abdominal trocars were inserted after obtaining sufficient pneumoperitoneum with a Veress needle (Ethicon Endo-surgery Inc., USA). Conventional laparoscopic 5 mm grasping forceps and scissors were used to perform the laparoscopic phase of the surgery. The peritoneum over the sacral promontory was incised (Figure 2a). At the vaginal phase of the surgery, a semi-circular incision was made at the posterior cervicovaginal junction. Curved ring forceps were introduced through with blunt dissection over the right sacrouterine ligament to establish a tunnel towards to the incised opening over the sacral promontory. This step was visualized simultaneously via laparoscopy (Figure 2b). A 15x3 cm, tailored, macroporous, non-absorbable polypropylene monofilament mesh (15cm-15 cm; Ethicon, Somerville, NJ, USA) was taken into the abdomen through the 10 mm trocar. When the ring forceps reached the incision at promontory level, the tip of the mesh was grasped and pulled down through the retroperitoneal tunnel until it came to the posterior cervix. The mesh was fixed to the posterior face of the uterine cervix using non-absorbable sutures through the vaginal route (Figure 2c). The semicircular vaginal incision was closed with absorbable sutures (Vicyrl 1; Ethicon, Somerville, NJ, USA) after attaching the mesh to the cervix. Finally, after uterine suspension was maintained with pushing the uterus to its normal position, the abdominal part of the mesh was sutured to the anterior longitudinal ligament at the sacral promontory with non-absorbable sutures using a laparoscopic technique (Figure 2d). The excess part of the mesh was cut with scissors and removed from the abdomen through a trocar. The peritoneal incision at the promontory level was closed with absorbable sutures to cover the fixated mesh (Figure 2e).

The VH+VVS operation was initiated with a circumferential incision in the vaginal epithelium at the junction of the cervix. After the dissection of the vaginal epithelium, we entered the abdominal cavity along the anterior and posterior planes of the uterus. Uterosacral and cardinal ligaments, uterine vessels, broad ligaments, and utero-ovarian pedicles were classically identified, clamped, cut, and ligated with absorbable sutures (Vicryl 1; Ethicon, Somerville, NJ, USA). The uterosacral ligaments were attached with absorbable sutures to the vaginal vault after hysterectomy for vaginal vault support. Sacrospinous ligament fixation surgeries were also performed for patients whose vaginal vaults were less than 2 cm from the hymen after vaginal hysterectomy. Finally, the vaginal cuff was closed by a running locking stitch with absorbable sutures.

Additional concomitant surgeries, including anterior and posterior colporrhaphy and perineoplasty, were performed after apical suspension, as needed. Additional anti-incontinence surgeries were performed in accordance with the patient–surgeon interviews after preoperative evaluation, including urodynamic examination. In daily practice, we perform a urodynamic examination before surgery for patients who have advanced uterine prolapse with or without complaints of stress urinary incontinence. However, in this case, the participants who had a confirmed diagnosis of stress urinary incontinence or were diagnosed with occult stress incontinence in the urodynamic study had anti-incontinence surgery suggested to them. Tension-free vaginal tape surgery was performed by a separate anterior mid-urethral incision if needed.

On the day of the operation, the allocation was confirmed, and appropriate consent was obtained for the given surgical procedures. Vaginal hysterectomy and laparoscopic hysteropexy were combined with anterior and/or posterior repair at the surgeon's discretion at the time of the operation. Each participant was initially followed-up with in the clinic at one week, one month, three months, and one year post-surgery as part of departmental procedure. Postoperative pain scores were evaluated 24 hours after surgery by a visual analog scale (VAS) score. Uterovaginal prolapse was assessed again using the International Consultation on Incontinence Questionnaire Vaginal Symptoms (ICIQ-VS) questionnaire and the Pelvic Organ Prolapse Quantification (POP-Q) system by another researcher, and then the operator. During interviews, further questions were asked regarding postoperative recovery, current urinary symptoms, and satisfaction with the operation. Subjective surgical outcome was measured using the Patient Global Impression of Improvement (PGI-I), which is a validated global index of response to prolapse surgery consisting of a seven-point scale upon which patients may compare their preoperative and postoperative conditions (with 1 being "very much better" and 7 being "very much worse").^[9] The PGI-I scale was evaluated one year after surgery with each of the patients.

The participants' prolapse symptoms, and their impacts, were evaluated both before and one year after surgical treatment. A subjective assessment of the prolapse was made using the ICIQ-VS.^[10] Objective assessment of pelvic organ prolapse was performed during a Valsalva maneuver using a Sims' speculum, and the frequently-used POP-Q scale was evaluated.^[11] Patients were also asked to complete the Urogenital Distress Inventory Short Form (UDI-6) and the Incontinence Impact Questionnaire Short Form (IIQ-7). The UDI-6 and IIQ-7 are accepted as validated questionnaires that are useful in the assessment of urogenital symptoms and disease-specific quality of life.^[12]

The measure for the primary outcome was treatment failure, defined as recurrent apical prolapse that required surgery within the first year after initial surgery. The secondary outcome measures were changed in anatomy quantified by POP-Q and symptoms quantified using the ICIQ-VS questionnaire scores for prolapse, quality of life, and PGI-I, UDI-6, IIQ-7 scores. Other secondary outcome measures were operation time, pain score, blood loss, and postoperative hospital stay.

Statistical analysis

Data analysis was performed with SPSS (version 20.0; Chicago, IL). Data were analyzed using descriptive statistical methods (mean, standard deviation, median, frequency, rate, minimum, and maximum). One sample Kolmogorov–Smirnov test was performed to analyze the distribution of the data. For group comparisons of parameters with quantitative data showing normal distribution, Student's t-test was used, while a Mann–Whitney U test was used for comparing other parameters not showing normal distribution. A p value of less than .05 was considered statistically significant.

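### Simple randomization with unadjusted comparisons leaves chance imbalance in pre-operative stage and stress incontinence uncorrected; the secondary analyses should adjust for both

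*Combined protocol and SAP*

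**What the plan says.** All references are to the combined protocol and SAP, whose sections are unnumbered.

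- **Allocation (Materials and Methods).** "Simple randomization was performed by the distribution of blind envelopes in order to separate the patients into the groups", and "this randomization was performed before admission to surgery". The allocation ratio is not given, and no blocks, strata or minimisation are mentioned.
- **Population (Materials and Methods).** Women were eligible with "stage 2–4 symptomatic uterine prolapse between June 2017 and January 2019", so entry severity varies by design. There is one centre.
- **Stress incontinence (Materials and Methods, concomitant surgery).** Urodynamic examination takes place before surgery. Women with confirmed stress incontinence, and those "diagnosed with occult stress incontinence in the urodynamic study had anti-incontinence surgery suggested to them", form a group identified before the operation and offered an extra procedure.
- **Outcomes.** The primary outcome is "treatment failure, defined as recurrent apical prolapse that required surgery within the first year after initial surgery". Secondary outcomes include POP-Q, ICIQ-VS, UDI-6, IIQ-7, operation time and blood loss.
- **Statistical analysis.** Quantitative outcomes are compared by Student's t-test or Mann–Whitney U. No covariate adjustment is planned, and no test is named for the binary primary outcome.

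The documents give no sample size, stage distribution, prevalence of stress incontinence or failure rate.

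**The concern.** A baseline factor that predicts outcome can be dealt with at two points: by restricting the randomization, or by adjusting the analysis. This plan does neither.

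Stage is a plausible predictor of the one-year POP-Q and ICIQ-VS results, and of apical recurrence. Incontinence diagnosis bears directly on UDI-6 and IIQ-7. Through added tape surgery it also bears on operation time and blood loss.

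If one arm happens to hold more stage 3–4 women or more tape candidates, an unadjusted comparison carries that difference into the estimate, and readers will question the result. Even when the arms are balanced, leaving out predictive baseline variables makes the intervals for the continuous outcomes wider than they need be.

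**Working it through.** There is no planned figure to reproduce, so the check asks how large chance imbalance could be over a range of assumed sizes.

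**Inputs.** From the documents: simple randomization and two arms. Assumed: 1:1 allocation; total N of 40, 60, 100 or 200; a binary factor present in 20 to 50% of women; a one-year failure rate of 2, 5 or 10%.

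**Arm sizes.** Under 1:1 simple randomization, the number in one arm is Binomial(N, 0.5).

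- P(35:25 or worse at N = 60) = 2 × P(X ≥ 35) = 24.5%.
- Information lost by unequal arms is 1 − 4f(1 − f), where f is the share in one arm. A 60:40 split gives 1 − 4 × 0.6 × 0.4 = 4%. A 35:25 split gives 1 − 4 × 35 × 25 / 60² = 2.8%. Unequal size alone costs little.

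**Imbalance in a factor.** Let m = prevalence × N women carry the factor. Carriers and non-carriers in arm A are independent Binomial(m, 0.5) and Binomial(N − m, 0.5). Exact enumeration gives the probability that the prevalence differs between arms by at least the stated amount:

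| | N = 40 | N = 60 | N = 100 | N = 200 |
|---|---|---|---|---|
| 30% factor, ≥ 10 points | 53% | 42% | 29% | 13% |
| 30% factor, ≥ 15 points | 32% | 22% | 10% | 2% |
| 30% factor, ≥ 20 points | 19% | 10% | 3% | 0.2% |
| 40% factor, ≥ 20 points | 23% | 13% | 5% | 0.4% |
| 20% factor, ≥ 20 points | 14% | 6% | 1.4% | < 0.1% |
| 50% factor, ≥ 20 points | 27% | 16% | 6% | 0.6% |

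A rough check: the standard deviation of the difference is about 2√(p(1 − p)/N). For p = 0.3 and N = 60 this is 2√(0.21/60) = 11.8 points, close to the exact 12.0.

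**Effect on the primary outcome.** The expected shift in the risk difference is the imbalance multiplied by the difference in failure risk between the levels of the factor. Take N = 60 (30 per arm) with 40% of women at stage 3–4.

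- Failure 5% versus 10%, imbalance 15 points: shift = 0.15 × 0.05 = 0.75 points. Overall risk is 0.05 + 0.4 × 0.05 = 7%, so SE = √(2 × 0.07 × 0.93/30) = 6.6 points. The shift is 0.11 SE.
- Failure 3% versus 12%, imbalance 20 points: shift = 0.20 × 0.09 = 1.8 points. Overall risk is 6.6%, so SE = 6.4 points. The shift is 0.28 SE.

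**Can the primary outcome be adjusted?** Expected events are N × rate. At failure rates of 2, 5 and 10% they are 1.2, 3 and 6 for N = 60; 2, 5 and 10 for N = 100; and 4, 10 and 20 for N = 200. At N = 60 the chance of even 10 events is below 0.1% at a 5% rate and 7% at a 10% rate. Adjustment is impractical if the trial is small and failure rare. With about 20 events, one or two covariates could be carried.

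**Can the secondary outcomes be adjusted?** Yes. Every woman with a one-year score contributes, so two binary covariates and a baseline value are affordable at any of these sizes. Prolapse symptoms and anatomy were assessed before surgery and again at one year. The text does not say outright that UDI-6 and IIQ-7 were also completed before surgery.

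**The case against.** The strongest reply is that nothing here is invalid. Simple randomization is unbiased, chance imbalance is part of the sampling error that the test and interval already allow for, and in an open single-centre surgical trial it is the least predictable scheme. The shift in the primary outcome is a fraction of a standard error even under unfavourable assumptions. Allocation is also over, so advice to stratify comes too late. All of this stands, and it limits the point to precision and credibility.

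It does not answer the lack of adjustment. For continuous outcomes, adjusting for pre-operative predictors narrows the interval and removes the imbalance at almost no cost.

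A reader might infer several stronger things that the documents do not support:

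- **That the trial is small and its primary event rare, so regression is impossible.** No size or event rate is given. One centre, about 19 months of recruitment and a one-year reoperation endpoint make this plausible, but do not establish it.
- **That stress incontinence predicts treatment failure.** Nothing in the text links it to apical reoperation. Its case rests on the secondary outcomes.
- **That women were excluded after allocation** because one criterion reads "cervical elongation (surgeon's discretion". It appears among the entry exclusions. The text does not date the judgement relative to the envelope, but gives no sign that it was made afterwards.
- **That reporting the primary outcome within stage would help.** A handful of events spread over four cells would show very little.

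**Conclusion.** The point holds as an analysis gap. Neither allocation nor analysis deals with chance imbalance in pre-operative stage or incontinence diagnosis, although both were evaluated before surgery.

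Its size depends on an unstated N. For a factor at 30 to 40% prevalence, a 20-point imbalance has probability 10 to 13% at 60 women, 3 to 5% at 100 and below 0.5% at 200. The exposure is therefore appreciable up to about 100 women and minor by 200. These figures assume 1:1 allocation and the stated prevalences.

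It would be wrong to read this as systematic bias or as a defect that invalidates the comparison. For the primary outcome the plausible distortion is small beside the sampling error. The gain from a change lies in the secondary outcomes.

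**What to change.** In the Statistical analysis section:

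1. Replace the unadjusted comparisons of one-year POP-Q, ICIQ-VS, UDI-6 and IIQ-7 with linear regression (ANCOVA) on arm. Adjust for pre-operative stage (2 versus 3–4), stress or occult stress incontinence diagnosis (yes/no) and, where collected, the baseline value of the same score.
2. Adjust operation time and blood loss for the same two factors, on a log scale if the residuals are skewed.
3. Use the pre-operative diagnosis as the covariate, not receipt of a tape, which follows allocation.
4. Tabulate stage and incontinence diagnosis by arm. For the primary outcome, state any residual imbalance as a limitation.
5. If outcomes have already been examined, say that the adjusted analyses were added afterwards and show the unadjusted results beside them.

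The cost is a little more analysis work on data that should already be in the patient records. The documents do not state that every woman had a urodynamic result, so the number without one should be reported.

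Stratified blocked allocation is relevant only to further recruitment. As an illustration, blocks of 4 within two strata of one factor would cap its imbalance at about 6.7 points for 60 women, at the price of some predictability near block ends.

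### Does the preference exclusion let randomised women leave the analysis according to the arm they drew?

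*Combined protocol and SAP*

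**What the plan says.** All of this is in the combined protocol and SAP, under Materials and Methods unless stated.

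- **Eligibility and consent.** Women first agree in principle and then receive fuller information, after which "consent was sought either in an outpatient clinic or at the next visit for preoperative assessment". Every participant gave written consent.
- **Allocation.** "Simple randomization was performed by the distribution of blind envelopes", and "this randomization was performed before admission to surgery".
- **Preference exclusion.** The next sentence opens: "Those who subsequently had a strong preference for either operation and consequently declined to continue in the study were excluded". Carried to its end, it says that those who "consequently declined to continue in the study were excluded and not put through the randomization process".
- **Day of surgery.** In the paragraph on the operation day and follow-up: "On the day of the operation, the allocation was confirmed, and appropriate consent was obtained for the given surgical procedures".
- **Primary outcome.** Treatment failure is "recurrent apical prolapse that required surgery within the first year after initial surgery".
- **Statistical analysis.** This section lists descriptive summaries, a check of distribution, two tests for comparing the groups and a .05 threshold. It names no analysis set and no rule for refusal, crossover or withdrawal after allocation.

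**The concern.** Three features together look like a route by which randomised women could be lost.

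First, the preference sentence comes straight after the one on randomisation. It speaks of a later preference and of declining to continue, which sounds like women already in the trial. Second, consent for the particular operation comes after allocation is confirmed, so a woman could refuse because of the arm she drew. Third, nothing says that women are analysed as randomised, and the outcome clock starts at surgery, so a woman who refuses surgery could drop out of the primary analysis unremarked.

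One operation keeps the uterus and the other removes it, and the text itself expects strong preferences. If refusals after allocation differed in number or type between the arms and those women were dropped, the groups would no longer be comparable by design. The patient-reported outcomes (PGI-I and ICIQ-VS) would be most exposed, since preference may be related to how a woman rates her result.

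**Working it through.** The plan states no sample size, power, event rate or refusal rate, so it has no figure to reproduce. The check is mainly one of reading the statements against each other.

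**1. Who does the preference sentence cover?** Its closing words say that the excluded women were not put through randomisation. A woman who was not randomised has no allocation, so her exclusion cannot depend on one. It affects to whom the results apply, not the comparison between arms.

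**2. Can the sentence's own time words be squared with that?** Yes. The eligibility paragraph gives an order: agreement in principle, fuller information, consent. A woman who agrees in principle, learns more, forms a preference and withdraws fits both *subsequently* and declining to continue, and she does so before any envelope is used. A preference for *either* operation also suits a woman who has not yet been assigned one. The reference point is not stated, so the sentence is ambiguous, but this reading leaves no contradiction.

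**3. Does operation-day consent add an exclusion rule?** No. It is surgical consent for a named procedure, separate from consent to the trial. It leaves room for a refusal after allocation, but it neither reports one nor says that such a woman is removed. Applying the preference exclusion to her would extend to randomised women a rule worded for women who were not randomised.

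**4. What of the surgery-based clock?** A woman who switches operation still has an initial surgery and hence a start date. Only a randomised woman who has no surgery lacks one, and recurrence after repair is not defined for her in any case.

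**5. How large could the effect be?** Every input here is an assumption: n = 40 per arm, failure risk p = 5%, refusal after allocation r = 5% to 10%.

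- Expected failures per arm: n × p = 40 × 0.05 = 2.
- Women refusing per arm: n × r = 40 × 0.05 = 2 up to 40 × 0.10 = 4.
- Expected failures among them, at the same risk: 2 × 0.05 = 0.1 up to 4 × 0.05 = 0.2.

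Setting 2 to 4 women lost against 2 events compares people with events. Like for like, it is 0.1 to 0.2 events against 2, a share of 5% to 10%. That share equals r whatever n and p are, because (n × r × p) / (n × p) = r. If the refusers' risk differed from the others', the figure would move, but the documents give nothing from which to say which way or how far.

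**The case for a change.** The strongest case for a change does not rely on the preference sentence alone. The Statistical analysis section is the whole statistical plan, and it is silent on the analysis set. The only statement anywhere about preference is one of exclusion, and nothing expressly protects a woman whose allocation is already known. Where the operations differ as much as these do, a sentence committing to analysis as randomised costs almost nothing, and an unstated policy leaves room for a choice made after seeing the data.

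Much of this stands. The timing of the preference exclusion could be clearer, the analysis set is unstated, and loss related to arm is not ruled out. It does not stand as a fault in the design or the analysis, because the documents neither prescribe nor describe such loss. A written rule would record the ordinary default for a two-group randomised comparison and would not alter any test.

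The practical gain is also small. Enrolment ran to January 2019, and the document is dated 10.01.2020 and reports first-year results in the past tense, so a new rule on follow-up would come too late for most women who refused. Nor can a later wording assert that exclusions came before the envelopes were opened unless that is what happened. The text cites a participant flow diagram, where exits would be shown. It is not reproduced in the available text, so its content cannot be called missing.

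**Conclusion.** The concern does not hold as a reason to change the plan. Read to its end, the preference sentence excludes women before randomisation, and operation-day consent carries no exclusion rule. The residue is missing detail: an unclear reference point for one word, and no named analysis set. A competent analyst fills it by comparing the groups as randomised and reporting any refusals by arm.

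No bias is demonstrated, and none can be sized from the documents. The 0.1 to 0.2 expected failures per arm rest wholly on assumed values and on refusers having the same risk as the others.

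The conclusion rests on two assumptions: that the closing words of the preference sentence describe what was done, and that women were compared in the groups to which they were allocated. If the flow diagram showed women removed after allocation because of preference, the question would reopen, as one about how the trial was conducted and reported.

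### UDI-6 and IIQ-7 are compared without adjustment, although preoperative scores and a preoperative stress-incontinence diagnosis appear to be available; adjusting is a cheap, optional gain in precision

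*Combined protocol and SAP*

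**What the plan says.** The outcome paragraph just before Statistical analysis lists, among the secondary outcomes, "quality of life, and PGI-I, UDI-6, IIQ-7 scores". The Statistical analysis section sets the method for quantitative outcomes: "For group comparisons of parameters with quantitative data showing normal distribution, Student's t-test was used". For the rest, a Mann–Whitney U "test was used for comparing other parameters not showing normal distribution". No covariate, regression, ANCOVA or stratified test is named. The opening paragraphs of Materials and Methods describe simple randomisation by envelopes, with no stratification factor.

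Two baseline items stand elsewhere in Materials and Methods:

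- **Preoperative scores.** The paragraph that introduces UDI-6 and IIQ-7 opens by saying that symptoms and their impact were assessed before surgery and again at one year. The sentence on the two questionnaires gives no time points of its own.
- **Stress-incontinence diagnosis.** In the paragraph on concomitant surgery, the investigators describe their daily practice: "we perform a urodynamic examination before surgery for patients who have advanced uterine prolapse with or without complaints of stress urinary incontinence". Anti-incontinence surgery was then suggested to "participants who had a confirmed diagnosis of stress urinary incontinence or were diagnosed with occult stress incontinence in the urodynamic study". Whether it was done depended on the discussion between patient and surgeon.

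**The concern.** UDI-6 and IIQ-7 measure urogenital symptoms and their effect on quality of life. A woman's preoperative score, and whether she has overt or occult stress incontinence, plausibly predict her one-year score whichever apical operation she receives. The diagnosis also governs who is offered a second, urinary operation. Occult incontinence is found on urodynamics rather than reported as a complaint, so the questionnaire score may not capture all of it.

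Because randomisation is simple and the tests are unadjusted, neither the design nor the analysis uses this information. Two things are at stake. The interval for the arm difference is wider than it need be. And if the arms happen to differ at baseline, part of the observed difference in urinary scores reflects that imbalance, with nothing in the analysis to remove it.

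**Working it through.** **Inputs.** The documents give no sample size, SD, prevalence of the diagnosis, or correlation between the diagnosis and these scores. There is therefore no figure of the plan's to reproduce, and every number below rests on a stated assumption.

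**1. Variance explained by the diagnosis alone.** Treat it as binary with prevalence p, and let d be the difference in mean one-year score between diagnosed and undiagnosed women, in within-group SDs. Then

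R² = p(1−p)d² / [1 + p(1−p)d²],

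and the sample size for a given precision falls by the fraction R².

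| d (SD) | R² at p = 0.2 | R² at p = 0.5 |
|---|---|---|
| 0 | 0 | 0 |
| 0.25 | 0.010 | 0.015 |
| 0.5 | 0.038 | 0.059 |
| 0.8 | 0.093 | 0.138 |
| 1.0 | 0.138 | 0.200 |
| 1.5 | 0.265 | 0.360 |

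Example: p = 0.3, d = 0.8 gives 0.21 × 0.64 = 0.134, and 0.134/1.134 = 0.118.

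**2. What that means for power.** Take a comparison with 80% unadjusted power at two-sided 0.05 (sidedness is not stated, so this too is assumed). Adjusted power is Φ[(1.96 + 0.84)/√(1−R²) − 1.96]: about 82% at R² = 0.05, 84% at 0.10, 88% at 0.20 and 94% at 0.36.

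**3. Increment over the baseline score.** If the baseline score is in the model, the relevant gain is what the diagnosis adds to it:

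(r_DY − r_BY·r_BD)² / (1 − r_BD²),

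where D is the diagnosis, B the baseline score and Y the one-year score. Assume r_BY = 0.5 and r_BD = 0.4. The baseline score alone then explains 0.5² = 25%.

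- p = 0.3, d = 0.8 (R² = 0.118, r_DY = 0.344): (0.344 − 0.20)²/0.84 = 0.025, or 2.5 points.
- p = 0.4, d = 1.0 (R² = 0.194, r_DY = 0.440): (0.440 − 0.20)²/0.84 = 0.069, or 6.9 points.
- p = 0.3, d = 0.5 (R² = 0.050, r_DY = 0.223): (0.223 − 0.20)²/0.84 = 0.0006, effectively nil.

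Under these assumptions most of the gain comes from the baseline score.

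**4. Chance imbalance.** With equal arms of 30 (assumed), the exact binomial probability that the arms differ by 20 points or more in prevalence is 12.0% at p = 0.3 and 14.7% at p = 0.4. At 50 per arm it is 3.8% and 5.2%. A 20-point imbalance shifts the unadjusted difference by 0.20 × d: 0.10 SD at d = 0.5, 0.16 at d = 0.8, 0.20 at d = 1.0. The standard error at 30 per arm is about √(2/30) = 0.26 SD, so each of these shifts is below one standard error.

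**The case against.** The strongest objection concerns the size of the gain. A reader might infer that the diagnosis is a strong predictor that drives one-year urinary scores. The documents do not support that: they report no association, and diagnosed women were offered treatment for that very condition, which may bring their one-year scores close to everyone else's. At d = 0 the diagnosis gives no gain. This objection stands, and it is why the range starts at zero.

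A reader might also infer that the unadjusted comparison is biased or has an inflated type I error. It is not. Under randomisation both tests are valid, and chance imbalance is already reflected in the standard error. What remains is that, in the one trial actually run, an imbalance is not corrected and precision is left unused.

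Three further objections concern feasibility, and all stand as conditions on the fix:

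- The diagnosis is not in the list of recorded variables near the start of Materials and Methods. Urodynamics is described as practice for advanced prolapse, while enrolment starts at stage 2, so a result for every participant is not assured.
- Randomisation took place before admission to surgery, but its order relative to urodynamics is not given. Adjusting for a diagnosis made with knowledge of the allocation could introduce bias.
- A plain linear model offers no counterpart to the Mann–Whitney test for skewed scores.

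**Conclusion.** The point holds as an optional improvement. The analysis of UDI-6 and IIQ-7 is valid but uses neither of two baseline items that are plausibly prognostic and appear to be available. The loss is in precision and in protection against chance imbalance, on two secondary outcomes among many. The primary outcome, repeat surgery for apical recurrence, is untouched.

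The size cannot be fixed from the documents. Across prevalence 20–50% and d from 0 to 1.5 SD, the diagnosis alone would explain 0–36% of the variance. Its contribution beyond the baseline score is smaller: roughly nil to 7 points in the three cases worked above, which rest on assumed correlations. The availability of preoperative UDI-6 and IIQ-7 scores is itself inferred from the opening of the paragraph that introduces them.

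**What to change.** In the Statistical analysis section, analyse one-year UDI-6 and IIQ-7 by ANCOVA with arm and the preoperative score of the same questionnaire. State whether the stress-incontinence diagnosis was recorded for all participants and whether it was made before, or blind to, allocation. If both hold, add it to the model as none / overt / occult; otherwise leave it out. Report the adjusted difference between arms with a 95% CI. If the scores are skewed, use robust or bootstrap intervals or a rank-based ANCOVA. Do not adjust for the tape actually placed: it is settled between patient and surgeon and may follow allocation.

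The cost is up to three degrees of freedom (one for the baseline score, two for the diagnosis) and extraction of the urodynamic result from clinical records. No new visit or measurement is needed if the preoperative scores were collected as the text implies.
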